14.3.1.2 Unsolicited Adverse Events

Table 409: All Adverse Events Cross-Classified by MedDRA System Organ Class, Severity, Relationship to Study Treatment, and Treatment Group

| | | | Relationship to Vaccination | | |
|-----------------|-------------------------------|----------|-----------------------------|-------------|------------------------|
| Treatment Group | MedDRA System Organ Class | Severity | Not Related (n) | Related (n) | Not Yet Determined (n) |
| Arm 2A (N=X) | Any SOC | Mild | | | |
| | | Moderate | | | |
| | | Severe | | | |
| | [Repeat for all reported SOC] | Mild | | | |
| | | Moderate | | | |
| | | Severe | | | |
| Arm 2B (N=X) | Any SOC | Mild | | | |
| | | Moderate | | | |
| | | Severe | | | |
| | [Repeat for all reported SOC] | Mild | | | |
| | | Moderate | | | |
| | | Severe | | | |
| Arm 2C (N=X) | Any SOC | Mild | | | |
| | | Moderate | | | |
| | | Severe | | | |
| | [Repeat for all reported SOC] | Mild | | | |
| | | Moderate | | | |
| | | Severe | | | |
| Arm 2D (N=X) | Any SOC | Mild | | | |
| | | Moderate | | | |

| Treatment Group | MedDRA System Organ Class | Severity | Relationship to Vaccination | | |
|-----------------|-------------------------------|----------|-----------------------------|-------------|------------------------|
| | | | Not Related (n) | Related (n) | Not Yet Determined (n) |
| | [Repeat for all reported SOC] | Severe | | | |
| | | Mild | | | |
| | | Moderate | | | |
| | | Severe | | | |
| Arm 2E (N=X) | Any SOC | Mild | | | |
| | | Moderate | | | |
| | | Severe | | | |
| | [Repeat for all reported SOC] | Mild | | | |
| | | Moderate | | | |
| | | Severe | | | |
| Arm 2F (N=X) | Any SOC | Mild | | | |
| | | Moderate | | | |
| | | Severe | | | |
| | [Repeat for all reported SOC] | Mild | | | |
| | | Moderate | | | |
| | | Severe | | | |
| Arm 2G (N=X) | Any SOC | Mild | | | |
| | | Moderate | | | |
| | | Severe | | | |
| | [Repeat for all reported SOC] | Mild | | | |
| | | Moderate | | | |
| | | Severe | | | |

| Treatment Group | MedDRA System Organ Class | Severity | Relationship to Vaccination | | |
|-----------------------|-------------------------------|----------|-----------------------------|-------------|------------------------|
| | | | Not Related (n) | Related (n) | Not Yet Determined (n) |
| Arm 2H (N=X) | Any SOC | Mild | | | |
| | | Moderate | | | |
| | | Severe | | | |
| | [Repeat for all reported SOC] | Mild | | | |
| | | Moderate | | | |
| | | Severe | | | |
| All Subjects (N=X) | Any SOC | Mild | | | |
| | | Moderate | | | |
| | | Severe | | | |
| | [Repeat for all reported SOC] | Mild | | | |
| | | Moderate | | | |
| | | Severe | | | |

Notes: N=Number of subjects in the Safety Population.
n=Number of events.

Table 410: Summary of All Unsolicited Adverse Events by MedDRA System Organ Class and Preferred Term, Severity, Relationship, and Treatment Group

| Treatment Group | System Organ Class (SOC) | Preferred Term (PT) | Total Events (n) | Severity | | | Relationship to Study Vaccination | | |
|------------------------------|-------------------------------|------------------------------|------------------|----------|--------------|------------|-----------------------------------|-------------|------------------------|
| | | | | Mild (n) | Moderate (n) | Severe (n) | Not Related (n) | Related (n) | Not Yet Determined (n) |
| Arm 2A (N=X) | Any SOC | Any PT | | | | | | | |
| | [SOC 1] | Any PT | | | | | | | |
| | | [PT 1] | | | | | | | |
| | | [Repeat for all reported PT] | | | | | | | |
| | [Repeat for all reported SOC] | Any PT | | | | | | | |
| | | [Repeat for all reported PT] | | | | | | | |
| Arm 2B (N=X) | Any SOC | Any PT | | | | | | | |
| | [Repeat for all reported SOC] | Any PT | | | | | | | |
| | | [Repeat for all reported PT] | | | | | | | |
| All Subjects (N=X) | Any SOC | Any PT | | | | | | | |
| | [Repeat for all reported SOC] | Any PT | | | | | | | |
| | | [Repeat for all reported PT] | | | | | | | |

Notes: N=Number of subjects in the Safety Population.
n=Number of events.

Table 411: Number and Percentage of Subjects Experiencing Unsolicited Adverse Events by MedDRA® System Organ Class and Preferred Term, Severity, Relationship, and Treatment Group

| | | | Severity | | | | | | | | Relationship to Study Vaccination | | | |
|------------------------------|-------------------------------|------------------------------|---------------|---|------|---|----------|---|--------|---|-----------------------------------|---|---------|---|
| | | | Any Incidence | | Mild | | Moderate | | Severe | | Not Related | | Related | |
| Treatment Group | MedDRA System Organ Class | MedDRA Preferred Term | n | % | n | % | n | % | n | % | n | % | n | % |
| Arm 2A (N=X) | Any SOC | Any PT | | | | | | | | | | | | |
| | [Repeat for all reported SOC] | Any PT | | | | | | | | | | | | |
| | | [Repeat for all reported PT] | | | | | | | | | | | | |
| | [Repeat for all reported SOC] | Any PT | | | | | | | | | | | | |
| [Repeat for all reported PT] | | | | | | | | | | | | | | |
| Arm 2B (N=X) | Any SOC | Any PT | | | | | | | | | | | | |
| | [Repeat for all reported SOC] | Any PT | | | | | | | | | | | | |
| | | [Repeat for all reported PT] | | | | | | | | | | | | |
| Arm 2C (N=X) | Any SOC | Any PT | | | | | | | | | | | | |
| | [Repeat for all reported SOC] | Any PT | | | | | | | | | | | | |
| | | [Repeat for all reported PT] | | | | | | | | | | | | |
| Arm 2D (N=X) | Any SOC | Any PT | | | | | | | | | | | | |
| | [Repeat for all reported SOC] | Any PT | | | | | | | | | | | | |
| | | [Repeat for all reported PT] | | | | | | | | | | | | |
| Arm 2E (N=X) | Any SOC | Any PT | | | | | | | | | | | | |
| | [Repeat for all reported SOC] | Any PT | | | | | | | | | | | | |
| | | [Repeat for all reported PT] | | | | | | | | | | | | |

| | | | Severity | | | | | | | | Relationship to Study Vaccination | | | |
|------------------------------|-------------------------------|------------------------------|---------------|---|------|---|----------|---|--------|---|-----------------------------------|---|---------|---|
| | | | Any Incidence | | Mild | | Moderate | | Severe | | Not Related | | Related | |
| Treatment Group | MedDRA System Organ Class | MedDRA Preferred Term | n | % | n | % | n | % | n | % | n | % | n | % |
| Arm 2F (N=X) | Any SOC | Any PT | | | | | | | | | | | | |
| | [Repeat for all reported SOC] | Any PT | | | | | | | | | | | | |
| | | [Repeat for all reported PT] | | | | | | | | | | | | |
| Arm 2G (N=X) | Any SOC | Any PT | | | | | | | | | | | | |
| | [Repeat for all reported SOC] | Any PT | | | | | | | | | | | | |
| | | [Repeat for all reported PT] | | | | | | | | | | | | |
| Arm 2H (N=X) | Any SOC | Any PT | | | | | | | | | | | | |
| | [Repeat for all reported SOC] | Any PT | | | | | | | | | | | | |
| | | [Repeat for all reported PT] | | | | | | | | | | | | |
| | [Repeat for all reported SOC] | Any PT | | | | | | | | | | | | |
| | [Repeat for all reported PT] | | | | | | | | | | | | | |
| All Subjects (N=X) | Any SOC | Any PT | | | | | | | | | | | | |
| | [Repeat for all reported SOC] | Any PT | | | | | | | | | | | | |
| | | [Repeat for all reported PT] | | | | | | | | | | | | |

Note: N=Number of subjects in the Safety Population.
n=Number of subjects reporting event with the specified SOC.
This table presents number and percentage of subjects. A subject is only counted once per PT and is summarized according to their highest severity and closest relationship.

14.3.2 Listing of Deaths, Other Serious and Significant Adverse Events

Table 412: Listing of Serious Adverse Events

| Adverse Event | No. of Days Post Associated Dose (Duration) | No. of Days Post Dose the Event Became Serious | Reason Reported as an SAE | Severity | Relationship to Study Treatment | If Not Related, Alternative Etiology | Action Taken with Study Treatment | Subject Discontinued Due to AE | Outcome | MedDRA System Organ Class | MedDRA Preferred Term |
|--|---|--|---------------------------|----------|---------------------------------|--------------------------------------|-----------------------------------|--------------------------------|---------|---------------------------|-----------------------|
| Subject ID: , Treatment Group: , AE Number: | | | | | | | | | | | |
| | | | | | | | | | | | |
| Comments: | | | | | | | | | | | |
| Subject ID: , Treatment Group: , AE Number: | | | | | | | | | | | |
| | | | | | | | | | | | |
| Comments: | | | | | | | | | | | |

Table 413: Listing of Non-Serious, Unsolicited, Moderate or Severe Adverse Events

| Adverse Event | No. of Days Post Vaccination (Duration) | Severity | Relationship to Vaccination | If Not Related, Alternative Etiology | Action Taken with Study Vaccination | Subject Discontinued Due to AE | Outcome | MedDRA® Sytem Organ Class | MedDRA® Preferred Term | Adverse Event |
|---|---|----------|-----------------------------|--------------------------------------|-------------------------------------|--------------------------------|---------|---------------------------|------------------------|---------------|
| Treatment Group: , Dose #: :, Subject ID, AE Number: | | | | | | | | | | |
| | | | | | | | | | | |
| Comments: | | | | | | | | | | |
| Treatment Group: , Dose #: :, Subject ID, AE Number: | | | | | | | | | | |
| | | | | | | | | | | |
| Comments: | | | | | | | | | | |

Table 414: Listing of AESIs, MAAEs, and NOCMCs

| Subject ID | Treatment Group | Event Description | Date of Product Administration ^a | Duration of Event | Date of Onset | MedDRA [®] System Organ Class | MAAEs | NOCMCs | Relationship ^b | Outcome |
|------------|-----------------|-------------------|---|-------------------|---------------|--|-------|--------|---------------------------|---------|
| | | | | | | | | | | |

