3. STUDY OBJECTIVES AND ENDPOINTS

3.1. Study Objectives and Endpoints

| OBJECTIVES | ENDPOINTS (OUTCOME MEASURES) |
|--|--|
| Primary | |
| 
 To evaluate the safety and reactogenicity of mRNA-1273 and mRNA-1273.351 vaccines, in naïve individuals. | 
 Frequency and grade of each solicited local and systemic reactogenicity AE during a 7-day follow-up period post each vaccination. Frequency and grade of any unsolicited AEs during the 28-day follow-up period post each vaccination. Frequency of any SAEs, Protocol Specified AESIs, NOCMCs, and MAAEs from the first vaccination through 12 months after the last vaccination. |
| Secondary | |
| 
 To assess humoral immunogenicity of mRNA-1273 and mRNA-1273.351 vaccines, in naïve individuals. | 
 Response rate, and magnitude of SARS-CoV-2-specific antibody binding and neutralization titers in serum samples as assessed via a range of assays at all timepoints. |
| Exploratory | |
| 
 To assess, in at least a subset of samples the innate immune response and B cell response following vaccination. | 
 Magnitude, phenotype, and percentage of innate immune cells and SARS-CoV-2 specific B cells, as measured by flow cytometry, and targeted B cell repertoire analysis at different timepoints post vaccination relative to baseline. |
| 
 To assess, in at least a subset of samples, the SARS-CoV-2 S protein-specific T cell responses. | 
 Magnitude, phenotype, and percentage of cytokine producing S protein-specific T cells, as measured by flow cytometry at different timepoints post vaccination relative to baseline. |

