9. SAFETY EVALUATION

Summaries and analysis of safety data will be presented for the Safety Analysis Population.

Solicited AEs will be summarized by severity for each day post vaccination (Days 1-8) for each dose and as the maximum severity over all 8 days. Additionally, solicited AEs will be analyzed by taking the most severe response over the follow-up period and using standard techniques, such as exact confidence intervals (CI), to summarize the proportion of subjects reporting each symptom, any local symptom, and any systemic symptom.

Unsolicited non-serious AEs will be collected from the time of the first vaccination through 28 days after the final vaccination. Unsolicited AEs will be coded by MedDRA for preferred term and system organ class (SOC). SAEs, Protocol Specified AESIs, MAAEs, and NOCMCs will be collected from the time of first vaccination through 12 months after the final vaccination. The numbers of SAEs and MAAEs will be reported by detailed listings showing the event description, MedDRA preferred term and SOC, relevant dates (vaccinations and AEs), severity, relatedness, and outcome for each event. Non-serious unsolicited AEs will be summarized as number and percentage of subjects reporting at least one event in each MedDRA preferred term and SOC, cross tabulated by severity and relationship to study product. Additionally, the proportion of subjects and exact 95% CIs of AEs in aggregate and by MedDRA categories will be computed.

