9.3.1. Solicited Events and Symptoms

Systemic solicited adverse events were collected pre-vaccination, and systemic and local solicited adverse events were collected 30 minutes post-vaccination and then daily for 7 days after the vaccination and graded on a scale of 0 (absent), 1 (mild), 2 (moderate) and 3 (severe). Systemic events include: fatigue, headache, myalgia, arthralgia, nausea, chills and fever. Local events include: pain at injection site, erythema, and induration.

For each systemic and local event, any systemic event, any local event, and any solicited event, the maximum severity over 7 days after the third vaccination will be summarized for the Safety population. The number and percentage of subjects reporting each event will be summarized by the maximum severity and treatment group (Table 389). For each event the denominator is the number of subjects with non-missing data for the specific event.

The number of subjects reporting a solicited adverse event will be summarized for each day post-vaccination both in a summary table (starting with Table 390 and ending with Table 407) and graphically in a bar chart (Figure 1250, Figure 1251, Figure 1252, Figure 1253, Figure 1254, and Figure 1255).

The mean, standard deviation, median, minimum and maximum duration of solicited events will be summarized (Table 408).

Day of solicited symptom onset will be summarized graphically (Figure 1256, Figure 1257, Figure 1258, Figure 1259, Figure 1260, and Figure 1261).

Solicited adverse events by subject will be presented in listings (Listing 10 and Listing 11) and graphically (starting with Figure 1262 and ending with Figure 1275).

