14.3 Safety Data

14.3.1 Displays of Adverse Events

Table 387: Overall Summary of Adverse Events by Treatment Group - All Subjects

| Subjects ^a with | | Arm 2A (N=X) | | Arm 2B (N=X) | | Arm 2C (N=X) | | Arm 2D (N=X) | | Arm 2E (N=X) | | Arm 2F (N=X) | | Arm 2G (N=X) | | Arm 2H (N=X) | | All Subjects (N=X) | |
|---|--------------------|-----------------|---|-----------------|---|-----------------|---|-----------------|---|-----------------|---|-----------------|---|-----------------|---|-----------------|---|-----------------------|---|
| Category 1 | Category 2 | n | % | n | % | n | % | n | % | n | % | n | % | n | % | n | % | n | % |
| At least one local solicited adverse event | NA | | | | | | | | | | | | | | | | | | |
| At least one systemic solicited adverse event | NA | | | | | | | | | | | | | | | | | | |
| At least one unsolicited adverse event | NA | | | | | | | | | | | | | | | | | | |
| At least one related unsolicited adverse event | Any Grade | | | | | | | | | | | | | | | | | | |
| | Mild (Grade 1) | | | | | | | | | | | | | | | | | | |
| | Moderate (Grade 2) | | | | | | | | | | | | | | | | | | |
| | Severe (Grade 3) | | | | | | | | | | | | | | | | | | |
| At least one severe (Grade 3) unsolicited adverse event | Any relationship | | | | | | | | | | | | | | | | | | |
| | Related | | | | | | | | | | | | | | | | | | |
| | Unrelated | | | | | | | | | | | | | | | | | | |
| At least one serious adverse event ^b | Any relationship | | | | | | | | | | | | | | | | | | |

| Subjects ^a with | | Arm 2A (N=X) | | Arm 2B (N=X) | | Arm 2C (N=X) | | Arm 2D (N=X) | | Arm 2E (N=X) | | Arm 2F (N=X) | | Arm 2G (N=X) | | Arm 2H (N=X) | | All Subjects (N=X) | |
|--|------------|-----------------|---|-----------------|---|-----------------|---|-----------------|---|-----------------|---|-----------------|---|-----------------|---|-----------------|---|-----------------------|---|
| Category 1 | Category 2 | n | % | n | % | n | % | n | % | n | % | n | % | n | % | n | % | n | % |
| | Related | | | | | | | | | | | | | | | | | | |
| | Unrelated | | | | | | | | | | | | | | | | | | |
| At least one adverse event leading to early termination ^c | N/A | | | | | | | | | | | | | | | | | | |
| Any Vital Signs Adverse Event | N/A | | | | | | | | | | | | | | | | | | |
| At least one medically attended adverse event | N/A | | | | | | | | | | | | | | | | | | |
| At least one new onset chronic medical condition | N/A | | | | | | | | | | | | | | | | | | |

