14.3.1.1 Solicited Adverse Events

Table 389: Number and Percentage of Subjects Experiencing Solicited Events by Symptom, Maximum Severity, and Treatment Group

| Symptom | Severity | Arm 2A (N=X) | | Arm 2B (N=X) | | Arm 2C (N=X) | | Arm 2D (N=X) | | Arm 2E (N=X) | | Arm 2F (N=X) | | Arm 2G (N=X) | | Arm 2H (N=X) | | All Subjects (N=X) | | |
|----------------------|----------|-----------------|---|-----------------|---|-----------------|---|-----------------|---|-----------------|---|-----------------|---|-----------------|---|-----------------|---|--------------------------|---|--|
| | | n | % | n | % | n | % | n | % | n | % | n | % | n | % | n | % | n | % | |
| Any Symptom | None | | | | | | | | | | | | | | | | | | | |
| | Mild | | | | | | | | | | | | | | | | | | | |
| | Moderate | | | | | | | | | | | | | | | | | | | |
| | Severe | | | | | | | | | | | | | | | | | | | |
| Any Systemic Symptom | None | | | | | | | | | | | | | | | | | | | |
| | Mild | | | | | | | | | | | | | | | | | | | |
| | Moderate | | | | | | | | | | | | | | | | | | | |
| | Severe | | | | | | | | | | | | | | | | | | | |
| Arthralgia | None | | | | | | | | | | | | | | | | | | | |
| | Mild | | | | | | | | | | | | | | | | | | | |
| | Moderate | | | | | | | | | | | | | | | | | | | |
| | Severe | | | | | | | | | | | | | | | | | | | |
| Fatigue | None | | | | | | | | | | | | | | | | | | | |
| | Mild | | | | | | | | | | | | | | | | | | | |
| | Moderate | | | | | | | | | | | | | | | | | | | |
| | Severe | | | | | | | | | | | | | | | | | | | |
| Fever ^a | None | | | | | | | | | | | | | | | | | | | |
| | Mild | | | | | | | | | | | | | | | | | | | |
| | Moderate | | | | | | | | | | | | | | | | | | | |
| | Severe | | | | | | | | | | | | | | | | | | | |

| | | Arm 2A (N=X) | | Arm 2B (N=X) | | Arm 2C (N=X) | | Arm 2D (N=X) | | Arm 2E (N=X) | | Arm 2F (N=X) | | Arm 2G (N=X) | | Arm 2H (N=X) | | All Subjects (N=X) | |
|-------------------|----------|-----------------|---|-----------------|---|-----------------|---|-----------------|---|-----------------|---|-----------------|---|-----------------|---|-----------------|---|--------------------------|---|
| Symptom | Severity | n | % | n | % | n | % | n | % | n | % | n | % | n | % | n | % | n | % |
| Feverishness | None | | | | | | | | | | | | | | | | | | |
| | Mild | | | | | | | | | | | | | | | | | | |
| | Moderate | | | | | | | | | | | | | | | | | | |
| | Severe | | | | | | | | | | | | | | | | | | |

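### The safety table shells do not match the stated primary safety endpoints: no AESI count or flag, Feverishness where the text lists chills, and no confidence intervals

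*SAP*

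**What the plan says.** SAP 3.1 gives three primary safety endpoints; two matter here. One is "Frequency of any SAEs, Protocol Specified AESIs, NOCMCs, and MAAEs from the first vaccination through 12 months after the last vaccination". The other is "Frequency and grade of each solicited local and systemic reactogenicity AE during a 7-day follow-up period post each vaccination".

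**AESIs.** Table 387, the overall AE summary by arm, has rows for SAEs and MAAEs and ends with "At least one new onset chronic medical condition". It has no AESI row. Section 9.4 sends AESIs to the listing "Table 414: Listing of AESIs, MAAEs, and NOCMCs", whose only category columns are MAAEs and NOCMCs.

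**Solicited terms.** Section 9.3.1 states: "Systemic events include: fatigue, headache, myalgia, arthralgia, nausea, chills and fever". The shells for Tables 389, 390 (the template for 391-407) and 408 have no chills row. Each carries a Feverishness entry, for example "Feverishness | None" in Table 389, in addition to Fever.

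**Intervals.** Section 9 says that "the proportion of subjects and exact 95% CIs of AEs in aggregate and by MedDRA categories will be computed". For solicited events, taken at their most severe over follow-up, it refers to standard techniques "such as exact confidence intervals (CI), to summarize the proportion of subjects reporting each symptom, any local symptom, and any systemic symptom".

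**The concern.** The appendix shells are what the programmers will build from. If they are followed as they stand, three things happen.

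- The report gives no AESI frequency by arm, although that frequency is part of a primary endpoint.
- The solicited systemic term list in the text and the one in the tables disagree. It is then unclear which seven terms feed the any-systemic-symptom rows, including their maximum severity.
- Proportions from arms of 15 or 20 subjects appear as n and % alone, without the uncertainty that Section 9 plans to show.

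**Working it through.** No figure in the SAP is in dispute. The check sets the text beside the shells, then shows what the absent intervals would contain.

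**1. Long-term event categories (3.1 against Tables 387 and 414)**

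| Category in 3.1 | Row in Table 387 | Identifiable in a listing |
|---|---|---|
| SAE | yes | yes, own listing (Table 412) |
| MAAE | yes | yes, column in Table 414 |
| NOCMC | yes | yes, column in Table 414 |
| AESI | no | only when neither other flag is set |

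Three of the four categories are counted by arm. Table 414 has a system organ class column but no preferred term, so the coded term cannot identify an overlapping AESI either.

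**2. Solicited terms (9.3.1 against Tables 389, 390 and 408)**

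- Systemic terms in 9.3.1, seven: fatigue, headache, myalgia, arthralgia, nausea, chills, fever.
- Systemic terms in the shells, seven: arthralgia, fatigue, fever, feverishness, headache, myalgia, nausea.
- Six agree. The seventh is chills in the text and feverishness in the shells.
- The three local terms (pain, erythema, induration) agree, so the mismatch affects 1 of 7 + 3 = 10 terms.

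These rows are not marked as illustrative. Where the SAP means examples it says so, as in the implementation notes to Tables 5 and 425. Tables 389, 390 and 408 have no such note.

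**3. Intervals (Section 9 against the safety table shells)**

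- Tables 387, 389, 390-407 and 411: n and % only.
- Table 388: n, % and event counts.
- Tables 409 and 410: event counts only.
- Elsewhere the shells do show planned intervals: Table 15 onward (geometric means), Tables 183-190 (T cells), Table 191 onward (fold rise and seropositivity) and Tables 383-386 (N-antibody and reported infection).

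**4. Size of what the intervals would show**

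The nearest safety figures in the SAP are the detection probabilities in Section 5 and Table 4, 1 - (1 - p)^n. They reproduce:

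- n = 15, p = 0.20: 1 - 0.8^15 = 96.5%
- n = 20, p = 0.20: 1 - 0.8^20 = 98.8%
- n = 150, p = 0.03: 1 - 0.97^150 = 99.0%

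For zero events the two-sided 95% Clopper-Pearson upper limit is 1 - 0.025^(1/n). For one event the limits are beta quantiles.

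| Events / n | Shown in shell | Exact 95% interval |
|---|---|---|
| 0/15 | 0% | 0 to 21.8% |
| 1/15 | 7% | 0.2 to 31.9% |
| 0/20 | 0% | 0 to 16.8% |
| 1/20 | 5% | 0.1 to 24.9% |
| 0/150 | 0% | 0 to 2.4% |

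The 21.8% for 0/15 does not contradict Section 5, which reads zero events as a rate below 20%. That reading is a one-sided statement at 96.5%, whereas the two-sided 95% interval leaves only 2.5% in the upper tail.

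**The case against.** The case on the other side has several parts, and most of them limit the point rather than remove it.

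- **AESIs are not lost.** Section 9.4 plans to list them, Table 414 shows treatment group and event description, and a row with neither an MAAE nor an NOCMC flag must be an AESI. This stands: only overlapping events are unidentifiable. But the endpoint is a frequency, and no shell gives one.
- **Chills may simply be mislabelled.** Seven terms face seven terms with one swap, which fits a label difference at least as well as an omission. This also stands. The document does not say which it is, so the text and the shells still conflict.
- **The solicited-event intervals are only an example.** The wording for these names exact intervals as one possible technique, and attaches them to the most severe response over follow-up. Daily columns in Table 390 therefore carry no such commitment. This stands. The sentence on AEs in aggregate and by MedDRA category is unconditional.
- **A missing column does not cancel the text.** Section 9 still specifies the method, and the Preface calls the mock-ups samples. True, but the same appendix does display intervals for the immunogenicity and N-antibody results, so their absence from the safety tables is likely to be followed literally.
- **Only the table shells could be checked.** The mock-ups for the safety figures and by-subject listings were not available, so the statement is confined to the safety tables.

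**Conclusion.** The shells and the text disagree in three places, and each bears on a primary safety endpoint or its planned analysis. One of four long-term categories has no count by arm. One of ten solicited terms is either unreported or mislabelled, which leaves the any-systemic-symptom composite ambiguous. The exact intervals planned in Section 9 have no place in the safety tables.

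A reader might infer more than this, and the document does not support it:

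- That AESIs are dropped: they are listed in Table 414.
- That chills was not collected or will certainly go unreported: it may have been recorded as feverishness.
- That intervals are firmly promised for every solicited-event table: the solicited wording is illustrative and does not reach the daily columns.
- That the intervals are themselves an endpoint component: they are a planned summary of one.

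The conclusion assumes that the reports will be programmed from the shells as printed. No method or estimate in the SAP is wrong; these are inconsistencies that should be corrected before programming.

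**What to change.** 1. Add a row to Table 387 for subjects with at least one AESI, in the same form as the MAAE and NOCMC rows, and add an AESI column to Table 414. A split by relationship is optional, since the MAAE and NOCMC rows have none.
2. Establish from the CRF or memory aid which term was collected. If chills, replace or supplement Feverishness in Tables 389-408 and check the matching figures. If feverishness, correct 9.3.1. If both, list both. State which terms make up the any-systemic-symptom rows.
3. Add Clopper-Pearson 95% intervals for the any-event proportions in Tables 387 and 411, and for the solicited-symptom proportions in Table 389. The daily columns of Table 390 and its copies do not need them.

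The cost is edits to shells and one sentence of text. No new data are needed.
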